### 3 ABBREVIATIONS

Abbreviations pertain to the SAP only (not the TFLs).

$\Delta\Delta\text{QTcF}$	placebo-corrected change-from-baseline QTcF
$\Delta\text{QTcF}$	change-from-baseline QTcF
ADaM	Analysis Data Model
AE	adverse event
$\text{AUC}_{0-t}$	area under the plasma concentration-time curve from time 0 to the time of the last observed concentration
BLQ	below the level of quantification
CDISC	Clinical Data Interchange Standards Consortium
$C_{\text{max}}$	maximum observed plasma concentration
CRU	Clinical Research Unit
CSR	Clinical Study Report
CV	coefficient of variation
EC	Early Clinical
ECG	electrocardiogram
HR	heart rate
ICH	International Conference on Harmonisation
NC	not calculated
NR	no result
PK	pharmacokinetic
QTc	QT interval corrected for heart rate
QTcF	Fridericia corrected QT interval
SAP	Statistical Analysis Plan
SD	standard deviation
SE	standard error
TEAE	treatment-emergent adverse event
TFLs	tables, figures, and listings
$T_{\text{last}}$	the time of the last observed plasma concentration
$T_{\text{max}}$	time of the maximum observed plasma concentration

## 4 INTRODUCTION

This SAP has been developed after review of the clinical study protocol (Final Version dated 11 April 2018).

This SAP describes the planned analysis of the safety, tolerability and PK data from this study. A detailed description of the planned TFLs to be presented in the Clinical Study Report (CSR) is provided in the accompanying TFL shell document.

Separate SAP describing all other planned analysis, including analysis of the ECG data will be produced by of iCardiac Technologies, Inc..

The intent of this document is to provide guidance for the statistical analyses of PK data. In general, the analyses are based on information from the protocol, unless they have been modified by agreement between NorthSea Therapeutics BV and Covance Early Clinical (EC) Biometrics. A limited amount of information concerning this study (eg, objectives, study design) is given to help the reader's interpretation. This SAP must be finalised prior to the lock of the clinical database for this study. When the SAP and TFL shells are agreed upon and finalised, they will serve as the template for this study's CSR.

This SAP supersedes the statistical considerations identified in the protocol; where considerations are substantially different, they will be so identified. If additional analyses are required to supplement the planned analyses described in this SAP, they may be performed and will be identified in the CSR. Any substantial deviations from this SAP will be agreed upon between NorthSea Therapeutics BV and Covance EC Biometrics and identified in the CSR.

This SAP is written with consideration of the recommendations outlined in the International Conference on Harmonisation (ICH) E9 guideline entitled, "Guidance for Industry: Statistical Principles for Clinical Trials" and the ICH E3 guideline entitled, "Guidance for Industry: Structure and Content of Clinical Study Reports."

## 5 STUDY OBJECTIVES

The primary objective of the study is:

- To evaluate the effects of therapeutic and suprathreshold concentrations of icosabutate on the Fridericia's corrected QT interval (QTcF) in healthy subjects (this will be a responsibility of iCardiac Technologies, Inc.).

The secondary objectives of the study are:

- To evaluate the effect of therapeutic and suprathreshold doses of icosabutate on other electrocardiogram (ECG) parameters (heart rate [HR], PR and QRS intervals, and T-wave morphology) in healthy subjects (this will be a responsibility of iCardiac Technologies, Inc.).

- To evaluate the PK of single doses of 600 mg and 2000 mg icosabutate in healthy subjects (this will be a responsibility of Covance EC Biometrics).
- To assess the safety and tolerability of single doses of 600 mg and 2000 mg icosabutate in healthy subjects (this will be a responsibility of Covance EC Biometrics).

## 6 STUDY DESIGN

This will be a Phase 1, single-centre, randomised, double-blind (except for moxifloxacin), placebo- and positive-controlled, 4-way crossover study assessing the ECG effects of therapeutic and supratherapeutic doses of icosabutate in healthy male and female subjects.

Thirty-two subjects will be randomised to 1 of 12 treatment sequences (Table 1), with approximately 3 subjects randomised into 8 of the 12 sequences, and 2 subjects randomised into 4 of the 12 sequences, and will receive a single oral dose of each of the following treatments, with a minimum 5-day wash-out between doses:

- therapeutic dose of icosabutate (600 mg)
- supratherapeutic dose of icosabutate (2000 mg)
- moxifloxacin (400 mg)
- placebo

[figure not shown]
Moxifloxacin will be used as a positive control to determine the assay sensitivity of this study, with an expected peak QT effect (placebo-corrected change-from-baseline QTcF [ $\Delta\Delta$ QTcF]) of 10 ms to 15 ms.

**Table 1: Treatment Sequences**

Treatment Sequence	Dosing Period			
	1 (Day 1)	2 (Day 6)	3 (Day 11)	4 (Day 16)
1	icosabutate (600 mg)	icosabutate (2000 mg)	placebo	moxifloxacin (400 mg)
2	icosabutate (2000 mg)	moxifloxacin (400 mg)	icosabutate (600 mg)	placebo
3	placebo	icosabutate (600 mg)	moxifloxacin (400 mg)	icosabutate (2000 mg)
4	moxifloxacin (400 mg)	placebo	icosabutate (2000 mg)	icosabutate (600 mg)
5	icosabutate (2000 mg)	placebo	icosabutate (600 mg)	moxifloxacin (400 mg)
6	placebo	moxifloxacin (400 mg)	icosabutate (2000 mg)	icosabutate (600 mg)
7	icosabutate (600 mg)	icosabutate (2000 mg)	moxifloxacin (400 mg)	placebo
8	moxifloxacin (400 mg)	icosabutate (600 mg)	placebo	icosabutate (2000 mg)
9	placebo	icosabutate (600 mg)	icosabutate (2000 mg)	moxifloxacin (400 mg)
10	icosabutate (600 mg)	moxifloxacin (400 mg)	placebo	icosabutate (2000 mg)
11	icosabutate (2000 mg)	placebo	moxifloxacin (400 mg)	icosabutate (600 mg)
12	moxifloxacin (400 mg)	icosabutate (2000 mg)	icosabutate (600 mg)	placebo

Subjects will be screened to assess their eligibility from Day -28 to Day -2. Subjects will be admitted to the Clinical Research Unit (CRU) on Day -1 and remain in the CRU until Day 18. Each subject will participate in 4 dosing periods, with doses administered in the morning of Days 1, 6, 11, and 16 after an overnight fast of at least 8 hours (not including water). Dose administration in each dosing period will be separated by a wash-out period of at least 5 days. There will be a Follow-up Visit 7 to 10 days after the final dose administration. An overview of the study design is shown in Figure 1.

**Figure 1: Study Schematic**

The total duration of study participation for each subject (from Screening through Follow-up Visit) is anticipated to be approximately 8 weeks.

## 7 TREATMENTS

The following is a list of the study treatment and ordering that will be used in the TFLs.

Study Treatment	Order on TFLs
600 mg icosabutate	1
2000 mg icosabutate	2
400 mg moxifloxacin	3
Placebo	4

The following is a list of the study treatment sequence abbreviations and ordering that will be used in the baseline TFLs.

Study Treatment Sequence	Abbreviation	Order on TFLs
600 mg icosabutate/2000 mg icosabutate/Placebo/400 mg moxifloxacin	A/B/C/D	1
2000 mg icosabutate/400 mg moxifloxacin/600 mg icosabutate/Placebo	B/D/A/C	2
Placebo/600 mg icosabutate/400 mg moxifloxacin/2000 mg icosabutate	C/A/D/B	3
400 mg moxifloxacin/Placebo/2000 mg icosabutate/600 mg icosabutate	D/C/B/A	4
2000 mg icosabutate/Placebo/600 mg icosabutate/400 mg moxifloxacin	B/C/A/D	5
Placebo/400 mg moxifloxacin/2000 mg icosabutate/600 mg icosabutate	C/D/B/A	6
600 mg icosabutate/2000 mg icosabutate/400 mg moxifloxacin/Placebo	A/B/D/C	7
400 mg moxifloxacin/600 mg icosabutate/Placebo/2000 mg icosabutate	D/A/C/B	8
Placebo/600 mg icosabutate/2000 mg icosabutate/400 mg moxifloxacin	C/A/B/D	9
600 mg icosabutate/400 mg moxifloxacin/Placebo/2000 mg icosabutate	A/D/C/B	10
2000 mg icosabutate/Placebo/400 mg moxifloxacin/600 mg icosabutate	B/C/D/A	11
400 mg moxifloxacin/2000 mg icosabutate/600 mg icosabutate/Placebo	D/B/A/C	12

## 8 SAMPLE SIZE JUSTIFICATION

A total of 32 subjects will be enrolled in order that a minimum of 28 subjects complete the study. Based on experience from the IQ CSRC study simulations to evaluate the power of small studies with exposure response analysis, and the observations from 25 recent TQT studies using exposure response analysis, a sample size of 28 will provide more than 95% power to exclude that icosabutate causes more than a 10 ms QTc effect at clinically relevant plasma levels, as shown by the upper bound of the 2 sided 90% confidence interval of the model predicted QTc effect ( $\Delta\Delta\text{QTcF}$ ) at the observed geometrical mean  $C_{\text{max}}$  of icosabutate in the study.

In addition to the evaluation through modelling and simulation, the sample size can be estimated approximately using a simple paired t-test for equivalence. Under the assumption that the QTc effect is 3 ms for icosabutate and 0 ms for placebo with a common standard deviation (SD) of change-from-baseline QTcF ( $\Delta\text{QTcF}$ ) of 8 ms for each treatment, and that 'No Effect' will be concluded if the 90% confidence interval of  $\Delta\Delta\text{QTcF}$  is lower than 10 ms, 28 subjects will provide >95% power with a one sided alpha of 5% in paired t-test. This estimation was performed using the paired t-test for equivalence of Means in R Version 3.2.5.

To demonstrate assay sensitivity with exposure-response analysis, it has to be shown that the  $\Delta\Delta\text{QTcF}$  of a single dose of 400 mg moxifloxacin exceeds 5 ms (ie, the lower bound of the 2-sided 90% CI of the predicted QT interval corrected for heart rate (QTc) effect [ $\Delta\Delta\text{QTcF}$ ] should exceed 5 ms). In a similarly designed recent crossover study with 24 healthy subjects, the standard error (SE) for the prediction of the QT effect of moxifloxacin based on the exposure-response analysis was 1.24 ms. The within-subject SD of change-from-baseline QTcF ( $\Delta\text{QTcF}$ ) in the referred study was 5.4 ms. If the effect of moxifloxacin is assumed to be 10 ms,

the SE of 1.24 ms corresponds to an effect size of  $\left( \frac{(10 - 5)}{(1.24 \times \sqrt{24})} \right) = 0.82$ , where the effect

size is the effect assumed under the alternative hypothesis divided by the SD of the test variable. In a one-sample t-test situation with a sample size of 24 subjects, this effect size results in a power of 98.8%. This value should be compared with the effect size of 0.57 required to guarantee a power of at least 90% in a one-sample t-test situation with a sample size of 28 subjects. Based on this calculation, a power of at least 90% will be obtained as long as the variability of  $\Delta\text{QTcF}$ , as measured by its SD, does not exceed 7.8 ms (ie, 144% of the 5.4 ms observed in the referred study).

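### Does the 8 ms SD in SAP Section 8 fail to support the stated power for icosabutate and for moxifloxacin assay sensitivity?

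*SAP*

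**What the plan says.** SAP Section 8 sets the size of the study: "A total of 32 subjects will be enrolled in order that a minimum of 28 subjects complete the study". It first supports 28 completers with exposure-response modelling and experience from earlier QT studies, and states more than 95% power on that basis. It then adds a paired t-test for equivalence, which it describes as an approximate estimate. The inputs are that "the QTc effect is 3 ms for icosabutate and 0 ms for placebo", a common SD of change-from-baseline QTcF "of 8 ms for each treatment", and a conclusion of no effect if the 90% confidence interval lies below 10 ms. The result is that "28 subjects will provide >95% power with a one sided alpha of 5% in paired t-test". Neither the SD of the paired difference nor the correlation between a subject's two changes is given.

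For assay sensitivity the same section argues from a reference crossover study of 24 subjects, with a model-based standard error of 1.24 ms and a within-subject SD of 5.4 ms. The starting point is worded "If the effect of moxifloxacin is assumed to be 10 ms", and the lower confidence bound must exceed 5 ms. The conclusion is a tolerance statement: "a power of at least 90% will be obtained as long as the variability of" the change from baseline, "as measured by its SD, does not exceed 7.8 ms (ie, 144% of the 5.4 ms observed in the referred study", stays within that limit.

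**The concern.** A paired t-test depends on the SD of the within-subject difference, and the SAP gives only a per-treatment SD. The reading that uses nothing beyond the stated inputs takes the two changes as independent, so the SD of the difference is 8√2 ms. Power then falls below the claimed figure. The assay-sensitivity argument appears to add to this: its SD ceiling of 7.8 ms is lower than the 8 ms that the same section has just assumed for what looks like the same variable, so the plan seems to break its own condition.

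If both readings were right, the section would overstate its chance of excluding a 10 ms effect and its chance of showing that the study can detect a QT effect. Those are the two results on which the primary objective rests. The SAP is also to serve as the template for the study report, so an unsupported figure could be carried forward.

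**Working it through.** **Inputs, all from SAP Section 8.** 28 completers (32 enrolled); one-sided alpha 5%; icosabutate effect 3 ms, limit 10 ms, so a distance of 10 − 3 = 7 ms; SD 8 ms per treatment; moxifloxacin effect 10 ms, threshold 5 ms, so a distance of 5 ms; reference study n = 24, SE 1.24 ms, within-subject SD 5.4 ms.

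**Icosabutate.** With correlation ρ between a subject's two changes, the SD of the difference is 8·√(2(1 − ρ)). Power is the upper tail of a noncentral t with 27 degrees of freedom and noncentrality 7/(SD of difference/√28), beyond the critical value 1.703.

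At ρ = 0: SD of difference = 8√2 = 11.31 ms; SE = 11.31/√28 = 2.138 ms; noncentrality = 7/2.138 = 3.274; power = 93.9%. Two one-sided tests with limits of ±10 ms also give 93.9%. A normal approximation gives 94.8%, and crossover degrees of freedom (54 or 81) give 94.4% to 94.5%.

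The result for other correlations, n = 28:

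| ρ | Power |
|---|---|
| 0 | 93.9% |
| 0.05 | 94.8% |
| 0.1 | 95.7% |
| 0.2 | 97.3% |
| 0.3 | 98.5% |
| 0.5 | 99.8% |

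Power reaches 95% when the SD of the difference is about 10.97 ms, that is at ρ of about 0.06, since 8·√(2 × 0.94) = 10.97. Taking 8 ms itself as the SD of the difference is the same as ρ = 0.5 and gives 99.8%. At ρ = 0, 30 completers give 95.2% and 32 give 96.2%.

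**Moxifloxacin, the plan's own figures first.** Effect size = 5/(1.24·√24) = 5/6.075 = 0.823 (stated 0.82). One-sample power at n = 24 is 98.8% (stated 98.8%). The effect size needed for 90% power at n = 28 is 0.5675 (stated 0.57). The SD ceiling is 5.4 × 0.823/0.5675 = 7.83 ms, or 5.4 × 0.82/0.57 = 7.77 ms with rounded inputs (stated 7.8). Power at 7.8 ms is 90.2%. Every figure reproduces.

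**Moxifloxacin at 8 ms, on the same scaling.** Effect size = 0.823 × 5.4/8 = 0.556; power at n = 28 is 88.9%, and at n = 32 it is 92.3%.

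**Whether the two SDs are the same kind.** The SAP calls only the 5.4 ms within-subject. If 8 ms is a total SD, the within-subject part is 8·√(1 − ρ). At ρ = 0.06 this is 8·√0.94 = 7.76 ms, below 7.8 ms. The correlation that brings the icosabutate power to 95% therefore also satisfies the moxifloxacin condition.

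**The case for a change.** The case for a change is that a strict figure above 95% is stated without the input that determines it. A reader cannot tell which calculation was run: one natural reading misses the figure, and the others depend on a number not in the SAP. The same missing definition leaves the 8 ms planning value outside the 7.8 ms ceiling, and a single sentence would settle both.

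The documentation point stands. The SD of the paired difference or the correlation should ideally have been written down, and the two SDs should have been labelled alike. The claim that two powers are wrong does not stand. The 93.9% needs zero correlation, which the SAP does not assume. The moxifloxacin sentence does not promise 90% power at 8 ms; it says how far the SD may rise above 5.4 ms before power drops below 90%, and it says so correctly. Its scaling is also not the √2 rule: the SD of the test variable there is 1.24·√24 = 6.07 ms, whereas 5.4·√2 = 7.64 ms. Setting the 8 ms directly against the 7.8 ms is therefore not shown to compare like with like.

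**Conclusion.** No change to the plan follows. The icosabutate power is under-documented rather than shown to be wrong. In the zero-correlation case it is 93.9%, about 1.1 points short of 95%, in a calculation that the SAP itself calls approximate and places beside a separate modelling argument. A correlation of about 0.06 or more closes the gap. The moxifloxacin statement holds as written; if 8 ms were a within-subject SD, power would be 88.9%, about 1.1 points under 90%. With all 32 enrolled subjects completing, even these least favourable readings give 96.2% and 92.3%.

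This rests on exact noncentral-t power with the SAP's stated inputs and, for moxifloxacin, on its own scaling from the reference study. The correlation is not in the SAP, so the range above is shown instead of one value. Supplying it would leave the enrolment, the analysis and the confidence-interval decision rules as they are, because planning power plays no part in those decisions.

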## 9 DEFINITION OF ANALYSIS POPULATIONS

The **Safety Population** will consist of all subjects who received at least 1 dose of study drug (icosabutate, moxifloxacin, placebo) and have at least 1 postdose safety assessment.

The **PK Population** will consist of all subjects who received at least 1 dose of study drug (icosabutate, moxifloxacin) and have evaluable PK data. A subject will be excluded from the PK summary statistics and statistical analysis if the subject has an adverse event (AE) of vomiting that occurs at or before 2 times median time of the maximum observed plasma concentration ( $T_{\text{max}}$ ), or important protocol deviations or AE thought to significantly affect the PK of icosabutate.

The **All Subjects Population** will be consistent with the Safety Population.

All protocol deviations that occur during the study will be considered prior to database lock for their severity/impact and will be taken into consideration when subjects are assigned to analysis populations. Details of subject assignment to the analysis populations will be listed.

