## 10 STATISTICAL METHODOLOGY

### 10.1 General

Data listings will be provided for the All Subjects Population. Summary statistics will be performed for subjects included in the relevant analysis populations (Safety/PK).

For continuous data, summary statistics will include the arithmetic mean, arithmetic standard deviation, median, minimum, maximum, and number. For log-normal data (eg, the PK

parameters: areas under the concentration-time curve [AUCs] and maximum observed plasma concentration [ $C_{max}$ ]), the geometric mean and geometric coefficient of variation (CV) will also be presented. For categorical data, frequency counts and percentages will be presented. Data listings will be provided for all subjects up to the point of withdrawal, with any subjects excluded from the relevant population highlighted. For the calculation of summary statistics unrounded data will be used.

Missing values will not be imputed.

Data analysis will be performed using SAS® Version 9.4.

Analysis Data Model (ADaM) datasets will be prepared using Clinical Data Interchange Standards Consortium (CDISC) ADaM Version 2.1, and CDISC ADaM Implementation Guide Version 1.1. Pinnacle 21 Community Validator Version 2.2.0 will be utilised to ensure compliance with CDISC standards.

Period day (day within the dosing period) will be used throughout all TFLs. It will be derived in the ADaM datasets (where applicable) and the mapping from study day to period day will be as follows.

	Dosing Period 1					Dosing Period 2					Dosing Period 3					Dosing Period 4		
Study Day	1	2	3	4	5	6	7	8	9	10	11	12	13	14	15	16	17	18
Period Day	1	2	3	4	5	1	2	3	4	5	1	2	3	4	5	1	2	3

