## 10.3 Pharmacokinetic Assessment

### 10.3.1 Pharmacokinetic Analysis

The following PK parameters will be determined where possible, from the plasma concentrations of icosabutate, using non-compartmental methods in validated software program, Phoenix WinNonlin (Certara, Version 6.4 or later):

Parameter	Definition
AUC 0-t	area under the plasma concentration-time curve from time 0 to the time of the last observed plasma concentration (T last ), calculated using the linear trapezoidal rule for increasing concentrations and the logarithmic rule for decreasing concentrations
C max	maximum observed plasma concentration
T max	time of the maximum observed plasma concentration

Additional PK parameters may be determined where appropriate.

The Cmax for moxifloxacin will be calculated by iCardiac Technologies, Inc.

Pharmacokinetic analysis will, where possible, be carried out using actual postdose times recorded in the raw data. If actual times are missing, nominal times may be used with Sponsor’s approval.

Concentrations are used as supplied by the analytical laboratory for PK analysis. The units of concentration and resulting PK parameters, with amount or concentration in the unit, will be presented as they are received from the analytical laboratory.

Both Cmax and Tmax will be obtained directly from the plasma concentration-time profiles.

For multiple peaks, the highest postdose concentration will be reported as  $C_{\max}$ . In the case that multiple peaks are of equal magnitude, the earliest  $T_{\max}$  will be reported.

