### 10.3.2 Criteria for Handling Concentrations Below the Limit of Quantification in Pharmacokinetic Analysis

- Concentration values that are below the level of quantification (BLQ) will be set to zero, with defined exceptions as follows;
  - Any embedded BLQ value (between 2 quantifiable concentrations) and BLQ values following the last quantifiable concentration in a profile will be set to missing for the purposes of PK analysis.
  - If there are late positive concentration values following 2 BLQ concentration values in the apparent terminal phase, these values will be evaluated. If these values are considered to be anomalous, they will be set to missing.
  - If an entire concentration-time profile is BLQ, the profile will be excluded from the PK analysis.
  - If a predose concentration is missing, these values may be set to zero for single dose studies and first dose of multiple dose studies with sponsor approval

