#### 10.3.2.1 Anomalous Values

- If a value is considered to be anomalous due to being inconsistent with the expected PK profile, it may be appropriate to exclude this point from the PK analysis. However, the exclusion of data must have strong justification and will be documented in the raw data and study report.
- Embedded BLQ values may be considered anomalous depending on the route of administration and the characteristics of the drug.
- PK parameters associated with positive predose value(s) greater than 5% of  $C_{\max}$  may be excluded from the summary statistics of PK tables and statistical analysis at the discretion of the pharmacokineticist.

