#### 10.3.4 Pharmacokinetic Statistical Methodology

No inferential statistical analysis will be performed.

PK parameters and plasma concentrations of icosabutate will be summarised by treatment and listed. Plasma concentrations will be graphically represented with an arithmetic mean plot and a concentration-time profile by subject (linear scale and semi-logarithmic scale).

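### The PK exclusion rule removes the whole subject, so an event in one icosabutate period also drops that subject's valid profile at the other dose.

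*SAP*

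**What the plan says.** SAP section 9 (Definition of Analysis Populations) puts the exclusion at the level of the subject: "A subject will be excluded from the PK summary statistics and statistical analysis if the subject has an adverse event (AE) of vomiting" at or before twice the median Tmax. An important protocol deviation, or an AE thought to affect icosabutate PK significantly, has the same consequence in the same sentence. The section does not name the period or treatment in which the event must occur.

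Section 10.1 (General) carries the same unit into the outputs: "Summary statistics will be performed for subjects included in the relevant analysis populations (Safety/PK".

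The design and presentation work at a finer level. Under section 6 (Study Design) each subject "will receive a single oral dose of each of the following treatments, with a minimum 5-day wash-out between doses", and both icosabutate doses are among those treatments. Section 10.3.4 then states: "PK parameters and plasma concentrations of icosabutate will be summarised by treatment and listed".

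Two other exclusion rules are also finer. Section 10.3.2 says: "If an entire concentration-time profile is BLQ, the profile will be excluded from the PK analysis". Section 10.3.2.1 allows the parameters tied to a predose value above 5% of Cmax to be left out, without removing the subject.

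**The concern.** The unit of exclusion does not match the unit of analysis. A subject who vomits early after one icosabutate dose has one compromised profile. The profile from the other dose, taken in a separate period after a wash-out, is not affected by that event. Under the rule as worded, both leave the summary statistics.

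A secondary objective is "To evaluate the PK of single doses of 600 mg and 2000 mg icosabutate in healthy subjects", and the descriptive per-dose presentation in section 10.3.4 is the only analysis this SAP plans for it. Valid data for one dose would be lost because of an event at the other.

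The time window is also loosely fixed. Icosabutate can be inferred as the analyte, since section 10.3.1 says "The following PK parameters will be determined where possible, from the plasma concentrations of icosabutate" and section 9 refers to the PK of icosabutate. The SAP does not say whether the median Tmax is taken per dose or pooled, or from which data. Read literally, even vomiting after moxifloxacin or placebo could remove a subject's icosabutate data.

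**Working it through.** No figure in the plan is at issue, so there is none to reproduce. The check has two parts: the text, then the size under stated assumptions.

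**Text**

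| SAP section | What is excluded or summarised | Unit |
|---|---|---|
| 9 | Vomiting, deviation or AE affecting PK | Subject |
| 10.1 | Who enters the summary statistics | Subject |
| 10.3.2 | Profile entirely BLQ | Profile |
| 10.3.2.1 | High predose value | Parameters |
| 10.3.4 | PK summaries | Treatment |

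The profile and parameter rules cover BLQ and predose values only, so they do not soften the section 9 rule. No other section narrows it.

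**Inputs.** n = 28 (planned minimum of completers) to n = 32 (enrolled), from section 8. Each subject contributes 2 icosabutate profiles, so 2n = 56 to 64 are planned. The number k of subjects with a qualifying event in one icosabutate period only is an assumption.

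**Loss by rule**
- Subject-level rule: 2k profiles.
- Period-level rule: k profiles.
- Needless loss: 2k − k = k.
- k = 0: no loss. A subject with events in both icosabutate periods loses 2 profiles under either rule, so nothing is needlessly lost.

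**All k events after the same dose.** The other dose loses a share k/n. At equal variability, the standard error of its log-mean grows by the factor √(n/(n − k)).

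| n | k | n left | k/n | √(n/(n − k)) |
|---|---|---|---|---|
| 28 | 1 | 27 | 3.6% | 1.018 |
| 28 | 2 | 26 | 7.1% | 1.038 |
| 28 | 4 | 24 | 14.3% | 1.080 |
| 32 | 1 | 31 | 3.1% | 1.016 |
| 32 | 2 | 30 | 6.3% | 1.033 |
| 32 | 4 | 28 | 12.5% | 1.069 |

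**Events split evenly between doses.** Each dose keeps n − k/2 under a period-level rule and n − k under the subject-level rule.
- n = 28: 27 against 26 for k = 2; 26 against 24 for k = 4.
- n = 32: 31 against 30 for k = 2; 30 against 28 for k = 4.

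**Cross-check with an event probability.** Let p be an assumed, independent probability of a qualifying event per icosabutate period. Expected profiles per dose are n(1 − p) under a period-level rule and n(1 − p)² under the subject-level rule. The needless loss over both doses is 2np(1 − p).

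| n | p | Period rule, per dose | Subject rule, per dose | Needless loss, both doses |
|---|---|---|---|---|
| 28 | 2% | 27.4 | 26.9 | 1.1 |
| 28 | 5% | 26.6 | 25.3 | 2.7 |
| 28 | 10% | 25.2 | 22.7 | 5.0 |
| 32 | 2% | 31.4 | 30.7 | 1.3 |
| 32 | 5% | 30.4 | 28.9 | 3.0 |
| 32 | 10% | 28.8 | 25.9 | 5.8 |

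For example, with n = 32 and p = 5%: 2 × 32 × 0.05 × 0.95 = 3.04.

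**The case against.** The best reply is that a period-level rule was meant. Vomiting timed against Tmax makes sense only relative to a particular dose, the summaries are by treatment, and the authors exclude by profile and parameter elsewhere. The deviation and AE triggers also involve judgement before database lock, which leaves room to ask which profile was affected. That intent is plausible, but it is not stated. Both section 9 and section 10.1 speak of subjects, and a programmer following them would drop both profiles. The unseen protocol is unlikely to settle it, because section 4 says the SAP supersedes the protocol's statistical considerations.

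Other points on that side stand:
- The SAP gives no event rate, so every non-zero k or p is assumed.
- No standard error or confidence interval is planned for PK, so the widening factors only indicate lost precision. The change in n is what the reader of the tables will see.
- Membership of the PK Population needs one dose and evaluable data, so n per dose is not tied to completers. The figures 28 and 32 are planning values.
- Listings and by-subject concentration plots are planned too, and excluded subjects are highlighted in the listings, so their data remain visible.
- The source of the median Tmax is a separate ambiguity, and its effect has not been quantified.

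**Conclusion.** The concern holds, as a minor point. Followed exactly, the rule discards one valid icosabutate profile for each subject whose qualifying event falls in only one icosabutate period. For one to four such subjects, all with events after the same dose, the other dose loses 3.1% to 14.3% of its profiles across n = 28 to 32. With no events, or with events in both icosabutate periods of the same subject, nothing is needlessly lost.

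The demonstrated effect is confined to the descriptive PK summaries. A shift in the geometric means cannot be shown from the document. The ECG analysis belongs to a separate SAP, and no effect on it is claimed.

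**What to change.** Keep the triggers and the factor of 2, and change the unit in section 9. Suggested wording:

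> Exclusion applies per subject and icosabutate dosing period. Icosabutate concentrations and PK parameters from a period are left out of the PK summary statistics only when the vomiting criterion, or the deviation/AE criterion, is met in that same period. The subject's other icosabutate profile is kept unless it meets a criterion itself. Vomiting in a moxifloxacin or placebo period does not by itself exclude icosabutate data. The reference for the vomiting window is the median icosabutate Tmax observed in this study for the dose given in that period.

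The last sentence is a secondary clarification. The sponsor may choose another reference, but the SAP should name it and say whether profiles affected by vomiting contribute to the median. The change of unit does not depend on that choice. Section 10.1 should also let the PK summaries follow the period-level flag.

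The cost is the SAP wording and a period-level PK exclusion flag in the analysis dataset. The n may then differ between the 600 mg and 2000 mg summaries, so it should be shown for each. Settling this before database lock avoids choosing between two readings once the events are known.
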